## 9.4 Demographic and Baseline Characteristics

Demographic (ie, age, age groups [< 65, > = 65 and < 75, and > = 75], sex, race, ethnicity) and baseline characteristics will be summarized by cohort and dose using descriptive statistics. If multiple races have been reported for a subject, the subject will be categorized as multiple race.

The baseline characteristics to be summarized included:

- Height
- Weight
- BMI
- ECOG status
- Number of previous lines of treatment
- Relapse vs. refractory status
- Type of lymphoma
- Transformed Disease (yes/no)
- Bulky disease (yes/no)

## 9.5 Efficacy Analyses

Due to early discontinuation of the study, limited efficacy data will be provided as tables and listings.

The proportion of subjects by best overall response and best overall response category will be presented. Response will be determined by Lugano Classification. The Lugano Classification response definitions for PET-CT evaluations of FDG-avid lymphomas uses the terminology CMR, PMR, NMR, or PMD. Corresponding designations from earlier response criteria include CR, PR, SD, or PD. Objective response includes CMR and PMR.

Other efficacy endpoints includes duration of response (DOR), progression-free survival (PFS) and overall survival (OS).

9.5.1 Analyses of Primary Efficacy Endpoint(s))

Not applicable for this study.

9.5.2 Analyses of Secondary Efficacy Endpoint(s)

Subject listings will be provided based on the available efficacy data.

Proportion of subjects with best overall response and by best overall response category will be presented. Response will be determined by Lugano classification

which includes complete metabolic response (CMR), partial metabolic response (PMR), no metabolic response (NMR) and progressive metabolic disease (PMD).

Proportion of subjects with an objective response of CMR or PMR per Lugano classification along with corresponding 90% CI will be calculated using Clopper-Pearson method.

DOR will be calculated only for subjects who achieve a best overall response of PMR or better. Subjects will be censored following the censoring strategy described in the definition of DOR. The distribution of DOR, including the median and quartiles will be characterized using the Kaplan-Meier(KM) method based on the subjects who achieve a best response of PMR or better. The 90% CIs for the median and quartiles of DOR will be constructed using the Brookmeyer and Crowley method.

The distribution of PFS, including median, will be estimated using the Kaplan-Meier method. The 90% CIs for the median and other percentiles of PFS will be constructed using the Brookmeyer and Crowley method.

OS will be analyzed using the same method as describe for the PFS endpoints.

9.5.3 Analyses of Exploratory Efficacy Endpoint(s)

Exploratory endpoints will not be analyzed with the limited scope of analysis for the discontinued study.

## 9.6 Safety Analyses

## 9.6.1 Dose Limiting Toxicities

Subject incidence of DLTs will be used to fit the BLRM model to estimate the probability of having a DLT across dose levels. Subject incidence of DLTs by SOC and PTs will be presented. A listing of DLTs occurring outside of the specified time interval will be produced to aid in determining if the sensitivity analysis should be conducted.

## 9.6.2 Adverse Events and Disease-related Events

The Medical Dictionary for Regulatory Activities (MedDRA) version 19 or later will be used to code all events categorized as adverse events to a system organ class and a preferred term.

The below adverse event tables will not be created if two or fewer subjects experience the adverse event.

The subject incidence of adverse events will be summarized by cohort and dose group for all treatment-emergent adverse events, treatment-emergent serious adverse events, treatment-emergent adverse events leading to interruption or withdrawal from investigational product or other protocol-required therapies, treatment-related treatmentemergent adverse events and fatal adverse events. The severity of each adverse event will be graded using CTCAE version 4.03 criteria.

Subject incidence of all treatment-emergent adverse events, treatment-emergent serious adverse events, treatment-emergent adverse events leading to interruption or withdrawal from investigational product, **treatment-emergent adverse events leading to dose reduction**, treatment-related treatment-emergent adverse events and fatal adverse events will be tabulated by system organ class and preferred term in descending order of frequency.

Subject incidence of disease-related events will be summarized for all treatment-emergent disease-related events by system organ class and preferred term.

Subject incidence of events of interest (standardized MedDRA queries and/or Amgen customized queries) when defined will also be summarized according to their categories and preferred term.

Details of each adverse event will be listed.

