### CONFIDENTIAL

reporting TEAEs will be evaluated overall and by dose level and will also be tabulated by relationship to study drug.

Tables of TEAEs serious TEAEs, TEAEs leading to withdrawal from investigational product or other protocol-required therapies, TEAEs that happen to  $\geq$  10% subjects, treatment related adverse events and fatal adverse events will also be provided.

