## 2. Objectives, Endpoints and Hypotheses

#### 2.1 Objectives and Endpoints

Objectives	Endpoints	
Primary		

 
Evaluate the safety and tolerability of AMG 562 in adult subjects with relapsed / refractory DLBCL, MCL, or FL
 
Estimate the maximum tolerated dose (MTD) and/or a biologically active dose (eg, recommended phase 2 dose [RP2D])
 
	Incidence of dose limiting toxicities (DLTs), treatment-emergent adverse events, treatment-related adverse events, disease-related events and clinically-significant changes in vital signs, physical examinations, electrocardiograms (ECG) and clinical laboratory tests	
Secondary		
Characterize the pharmacokinetics (PK) of AMG 562	
 
AMG 562 PK parameters including, but not limited to, maximum concentration (Cmax), minimum concentration (Cmin), time of maximum concentration (Tmax), area under the concentration-time curve (AUC), and if feasible, half-life (t1/2)
 
	
Evaluate anti-lymphoma activity of AMG 562	
 
ORR according to Lugano classification
 
Best Overall response by category. [Response terminology reflects the response criteria used. The Lugano Classification response definitions for positron emission tomography-computed tomography (PET-CT) evaluations of fluorodeoxyglucose (FDG)-avid lymphomas uses the terminology complete metabolic response (CMR), partial metabolic response (PMR), no metabolic response (NMR), or progressive metabolic disease (PMD). Corresponding designations from earlier response criteria include complete response (CR), partial response (PR), stable disease (SD), or progressive disease (PD)]
 
Duration of response (DOR)
 
	

	Progression free survival (PFS)	
	Overall survival (OS)	
Exploratory		
Evaluate the formation of anti-AMG 562     antibodies	Incidence of anti-AMG 562 antibody     formation	

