## 9.7.4 Analyses of Biomarker Endpoints

## Not applicable due to restricted scope of analysis post the discontinuation of the study.

#### 10. Changes From Protocol-specified Analyses

To restrict the scope of analysis post the discontinuation of the study, following changes were made in the reporting of results from protocol-specified analysis:

- Primary analysis to include the reduced set of analyses at time of decision to terminate the study. Final analysis will include the follow-up for the single patient still receiving treatment.
- Analysis of exploratory endpoints will not be performed.
- Probability of each TPI and DLT will not be summarized.
- A summary of the change from baseline to the post dose maximum, time to postdose maximum, change from baseline to the post dose minimum, and the time to the post dose minimum will not be provided for selected laboratory parameters of interest.
- Shift tables indicating the change between the baseline and the maximum post dose CTCAE grades for an increased value, and the maximum post dose grade for a decreased value will not be provided for selected laboratory parameters of interest.

- The number and percentage of subjects experiencing treatment emergent laboratory toxicities with worst post dose CTCAE grades of 1, 2, 3 and 4 will not be presented.
- A listing of laboratory toxicity grade 3 or higher will not be provided.
- Vital signs listing will not be provided.
- Summary and shift table for ECOG will not be provided.
- ECG listing will not be provided.
- Analysis of biomarker endpoints will not be performed.

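### SAP 9.6.2 withholds adverse event tables at two or fewer subjects, with no exemption for serious, fatal or treatment-related events, no stated level for the count, and no entry in Section 10

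*SAP*

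**What the plan says.** SAP Section 9.6.2 places this sentence ahead of its table specifications: "The below adverse event tables will not be created if two or fewer subjects experience the adverse event". The tables that follow cover all treatment-emergent adverse events, serious events, events leading to interruption or withdrawal, events leading to dose reduction, treatment-related events and fatal events. They are to be summarised by cohort and dose group, and the section adds that "treatment-related treatment-emergent adverse events and fatal adverse events will be tabulated by system organ class and preferred term in descending order of frequency". No category is exempt from the threshold.

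Two outputs are unaffected. The same section ends with "Details of each adverse event will be listed", and Section 9.6.1, which comes before the rule, says "Subject incidence of DLTs by SOC and PTs will be presented".

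SAP Section 2.1 defines the primary endpoint as "Incidence of dose limiting toxicities (DLTs), treatment-emergent adverse events, treatment-related adverse events, disease-related events" together with clinically significant changes in other safety measures.

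Protocol Section 10.5.2 (Adverse Events) commits to tables of serious events, events leading to withdrawal, events in at least 10% of subjects and, in its words, "treatment related adverse events and fatal adverse events will also be provided". It sets no minimum count for the serious, withdrawal, related or fatal tables. SAP Section 10 introduces its list of departures with "following changes were made in the reporting of results from protocol-specified analysis". The list goes down to dropped vital-sign and ECG listings but does not contain the two-subject rule.

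**The concern.** The primary endpoint is incidence, so its natural output is a count over a denominator by dose. The rule can remove that output where counts are small. In a first-in-human study that stopped early, with cohorts of 1 or of 3 to 4 subjects (Protocol synopsis, Table 1 and Dose Exploration), small counts are the normal case and two subjects can be a large fraction.

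The sentence also has no defined level. Its subject is the table, but the event is in the singular and the tables are by cohort and dose group. Two programmers could therefore implement different rules. Finally, a missing table cannot be told apart from a category in which nobody had an event.

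**Working it through.** **1. What each reading does.**

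- *Per table (the literal wording).* A table is skipped when two or fewer subjects have any event in that category. With one or two fatal events there is no fatal table; the same holds for the serious, related, withdrawal and dose-reduction tables. The term still appears in the all-event table by system organ class and preferred term, provided at least three subjects had any treatment-emergent event. Nothing specified for that table marks the term as fatal, serious or related.
- *Per preferred term.* A term seen in one or two subjects drops out of every table under the rule.
- *Per cohort.* A single-subject cohort could never qualify. In cohorts of 3 or 4 the rule would leave out observed rates up to 2/3 = 67% or 2/4 = 50%.

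**2. The plan's own figures.** SAP Section 3.2 gives the chance of seeing at least one event with n = 55. The formula is P(X≥1) = 1 − (1−p)^n.

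- p = 1%: 1 − 0.99^55 = 42.5% (stated 43%).
- p = 5%: 1 − 0.95^55 = 94.0% (stated 94%).

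The binomial model therefore matches the plan's own to within a percentage point.

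**3. The effect of the threshold.** The relevant quantity is the chance that an event type occurs but in only one or two subjects:

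P(1≤X≤2) = n·p·(1−p)^(n−1) + [n(n−1)/2]·p²·(1−p)^(n−2)

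Actual N is not in the documents (SAP Section 1 says only that the study ended earlier than planned), so N = 10, 15 and 30 are assumptions, as are all the rates.

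| N | rate | P(X=1) | P(X=2) | P(1≤X≤2) | P(X≥1) | share of occurrences seen in only 1–2 subjects |
|---|---|---|---|---|---|---|
| 10 | 20% | 0.268 | 0.302 | 57% | 89% | 64% |
| 15 | 15% | 0.231 | 0.286 | 52% | 91% | 57% |
| 30 | 5% | 0.339 | 0.259 | 60% | 79% | 76% |

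At n = 55 and a 5% rate, the chance of reaching three subjects is 52%, against the 94% chance that the event occurs at all.

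**4. Where these figures apply.** They give the chance of a missing table only if the event type is the whole category (for example, any fatal event) or if the rule works per term. They do not give the chance that the serious table disappears unless the rate is that of having any serious event.

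**5. What two subjects means as a rate.** 2/10 = 20%; 2/15 = 13.3%; 2/30 = 6.7%; 2/55 = 3.6%. The threshold marks a low rate only when N is large.

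**The case against.** The strongest reply is that this concerns format, not data.

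- **Nothing goes unrecorded.** Every adverse event is listed and dose-limiting toxicities are tabulated by term with no threshold. Potential Hy's law cases and laboratory toxicity grades are summarised separately (SAP Section 9.6.3). This stands.
- **Denominators exist.** SAP Section 9.2 reports the number who received investigational product by cohort and dose, so a reader can set a listed event against its denominator. This stands, but the reader would then be assembling the primary endpoint by hand.
- **The literal reading is per table.** A rare term would usually still be in the all-event table, and in the serious or related table whenever at least three subjects fall in that category. This stands. It does not help the fatal table, or any key category with one or two subjects.
- **Reduced reporting is disclosed in general terms.** SAP Section 1 and the first item of Section 10 say that the analysis set was cut back. This is partly right: the specific rule is not named, although smaller changes are.
- **The protocol's promise is narrower than the SAP's list.** It names withdrawal, not interruption or dose reduction. This stands, and the departure from the protocol should be read accordingly.

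A reader might infer that rare serious, fatal and related events vanish from the safety tables altogether. The documents do not support that: it would need a per-term or per-cohort count, which the SAP neither states nor excludes, and the listing remains in any case.

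A reader might also quote P(X≤2), which is 68%, 60% and 81% for the three scenarios in the working. Those figures count zero events as suppressed, so they overstate the effect.

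**Conclusion.** The point holds as a gap in summary reporting. As written, SAP Section 9.6.2 can leave serious, fatal, related or withdrawal events without a by-dose incidence table when one or two subjects are affected. It departs from Protocol Section 10.5.2 without being listed in SAP Section 10, and it leaves open the level at which the count is taken. It does not remove events from the record and does not touch the tabulation of dose-limiting toxicities.

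Under the assumed N and rates, an event type has a 52% to 60% chance of occurring in only one or two subjects. This bears on a table directly only for a whole category or under a per-term rule. The conclusion about the text needs no assumption about N; only the size does. The sentence should be corrected, because the affected outputs belong to the primary endpoint and the correction is cheap.

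**What to change.** Either delete the sentence, or do all three of the following:

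1. Exempt the serious, fatal, treatment-related and withdrawal tables, so that they are produced by dose and overall whatever the count.
2. For any table still under the threshold, state whether the count is taken per table, per preferred term or per cohort.
3. Add the rule to SAP Section 10 as a change from Protocol Section 10.5.2.

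The cost is an edit to one sentence, one added item in Section 10 and a few short tables. No new data are needed, and no table types beyond those the SAP already specifies.

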#### 9.6.3 Laboratory Test Results

The selected laboratory parameters of interest include: platelets, white blood cell, hemoglobin, absolute neutrophil count, lymphocyte, AST, ALT, total bilirubin, alkaline phosphatase, PT or INR, PTT, amylase, lipase, LDH, uric acid, immunoglobulins .

Summaries of the absolute value and/or changes and percentage changes from baseline at each scheduled assessment will be provided by cohort and dose.

## Additionally, summary of toxicity grades will be provided for laboratory analytes for which CTCAE grades are available by cohort and dose .

Potential Hy's law cases will be summarized. A Hy's Law case is defined as: AST or ALT values of  $\geq$  3x ULN AND with serum total bilirubin (TBIL) level of > 2x ULN or INR > 1.5 without signs of cholestasis and with no other clear alternative reason to explain the observed liver-related laboratory abnormalities

#### 9.6.4 Vital Signs

Summary statistics for each vital sign parameter (e.g., systolic / diastolic blood pressure, heart rate, respiratory rate, temperature and pulse oximetry )will be provided for baseline and each scheduled post-baseline assessment. summaries of changes and percentage changes from baseline over time will be provided at scheduled time points as per protocol.

## 9.6.5 Physical Measurements

Subject's weight, height and BMI will be presented as part of baseline characteristics.

## 9.6.6 Electrocardiogram

Where multiple ECG measurements are taken at the same assessment the mean value will be calculated and used in the analysis. For baseline ECG, mean value of the three triplicates will be calculated and used in the analysis. The mean of the values within a triplicate should be calculated before taking the mean of the triplicate averages.

For pre and post dose ECG measurements, unscheduled ECG measurements taken up to 5 minutes after the last assessment of a triplicate will be included in the average for a time point. Where an ECG is missing within a triplicate, all available data will be averaged for that time point.

Summaries over time and/or changes and percentage changes from baseline over time will be provided for all ECG parameters at scheduled time points as per protocol.

## 9.6.7 Antibody Formation

The incidence and percentage of subjects who develop anti-AMG 562 antibodies (binding and/or neutralizing) at any time **may** be summarized by cohort and dose. Positive anti-AMG 562 antibody data will be reviewed for each subject. Summaries of positive anti-AMG 562 antibody test results over time may be provided.

## 9.6.8 Exposure to Investigational Product

Details for each AMG 562 administration will be reviewed for every subject. In addition a listing of the unique manufacturing lot numbers, and a listing of the subjects administered each manufacturing lot number will be provided.

#### 9.6.9 Exposure to Concomitant Medication

The number and proportion of subjects receiving therapies of interest will be summarized by preferred term or category as coded by the World Health Organization Drug (WHO DRUG) dictionary.

#### 9.7 Other Analyses

## 9.7.1 Analyses of Pharmacokinetic or Pharmacokinetic/Pharmacodynamic Endpoints

The PK analyses will be performed by CPMS group.

Serum concentrations of AMG 562 will be determined using a validated assay.

PK parameters will include, but are not limited to maximum observed concentration ( $C_{max}$ ), minimum observed concentration ( $C_{min}$ ) and area under the concentration-time curve over the dosing interval [AUC] and if feasible half-life ( $t_{1/2}$ ). Pharmacokinetic parameters will be estimated using standard non-compartmental approaches based on the PK analysis set and summarized by dose level using means, standard deviations, medians, minimums, and maximums.

Serum concentrations below the lower limit of quantification will be set to zero for the estimation of the pharmacokinetic parameters for each subject and for the calculation of the summary statistic for each time point. Actual dosing and sampling time will be used for all calculations. The reasons for excluding any sample from the analyses will be provided.

Individual concentration-time data will be summarized by dose level. Individual concentration-time data will also be tabulated and presented graphically. Summary statistics will be computed for each sampling time and parameter as appropriate.

Additional PK analyses, including but not limited to analysis of the relationship between AMG 562 dose and exposure parameters (AUC and  $C_{max}$ ) and dose proportionality assessments, may also be conducted.

## 9.7.2 Analyses of Clinical Outcome Assessments

Not applicable for this study.

## 9.7.3 Analyses of Health Economic Endpoints

Not applicable for this study.

## 9.7.4 Analyses of Biomarker Endpoints

## Not applicable due to restricted scope of analysis post the discontinuation of the study.

#### 10. Changes From Protocol-specified Analyses

To restrict the scope of analysis post the discontinuation of the study, following changes were made in the reporting of results from protocol-specified analysis:

- Primary analysis to include the reduced set of analyses at time of decision to terminate the study. Final analysis will include the follow-up for the single patient still receiving treatment.
- Analysis of exploratory endpoints will not be performed.
- Probability of each TPI and DLT will not be summarized.
- A summary of the change from baseline to the post dose maximum, time to postdose maximum, change from baseline to the post dose minimum, and the time to the post dose minimum will not be provided for selected laboratory parameters of interest.
- Shift tables indicating the change between the baseline and the maximum post dose CTCAE grades for an increased value, and the maximum post dose grade for a decreased value will not be provided for selected laboratory parameters of interest.

- The number and percentage of subjects experiencing treatment emergent laboratory toxicities with worst post dose CTCAE grades of 1, 2, 3 and 4 will not be presented.
- A listing of laboratory toxicity grade 3 or higher will not be provided.
- Vital signs listing will not be provided.
- Summary and shift table for ECOG will not be provided.
- ECG listing will not be provided.
- Analysis of biomarker endpoints will not be performed.

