# **Dose Limiting Toxicities**

Subject incidence of DLTs will be used to fit the BLRM model to estimate the probability of having a DLT across dose level. Adverse Events

Subject incidence of all treatment-emergent adverse events (TEAEs) will be tabulated by system organ class and preferred term. The number and percentage of subjects

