#### 3.3 Adaptive Design

A two-parameter Bayesian Logistic Regression Model (BLRM) is used to guide dose exploration. The MTD target Toxicity Probability Interval (TPI) for DLT is (0.20, 0.33] and TPIs of (0.33, 0.60] and (0.60, 1.00] are defined as excessive and unacceptable, respectively. The design seeks to identify a dose most likely to have a DLT rate in the target TPI, but with overdose control that limits the possibility the dose has an excessive or unacceptable DLT rate (Babb et al, 1998). The probability of a DLT at dose level di is assumed to follow a Bernoulli distribution with probability pi where the logit of pi increases linearly with the log of the standardized dose in the following 2-parameter logistic model:

 $\log [p_i / (1-p_i)] = \log (p_i) = \log [a] + \exp(\log [b]) \log (d_i / d_{ref})$ 

where a and b are random variables and  $d_{ref}$  is 1 of the planned dose selected as the reference dose.

A bi-variate normal prior distribution (Neuenschwander et al, 2008) was selected for theta = (log a, log b) where the probability that the true DLT rate is  $\leq$  0.40 at the lowest planned dose is **and** the probability the true DLT rate is  $\leq$  0.05 at the reference dose is 0.05. These values were selected such that pi is 0.01 for the starting dose and 0.40 for the reference dose (**m** µg).

The operating characteristics of the two-parameter BLRM design were evaluated via simulation using EAST version 6.4.1. The cohort size was fixed to 3 or 4 subjects. All simulated studies start with the multiple subject cohorts. The initial multiple subject dose level is  $\mu$ g and subsequent doses were selected based on the following rules:

After each cohort, the next dose is the one with the highest probability of the target TPI, but with a less than 0.40 probability of an excessive or unacceptable TPI.

Dose exploration will continue until any of the following events.

- The highest planned dose level is determined to be safe and tolerable (minimum of 6 treated subjects)
- An MTD is identified where BLRM repeats the recommendation of a dose level (minimum of 6 treated subjects)
- If fewer than 6 subjects are treated at the MTD/RP2D, additional subjects may be enrolled to confirm safety and tolerability.

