## Maximum Tolerated Dose (MTD)

An estimate of the MTD will be made based on a Bayesian Logistic Regression Model (BLRM) utilizing all DLT-evaluable subjects from the dose exploration and dose expansion cohorts. Based on the BLRM, the MTD is defined as the dose with the highest probability of a DLT rate between the targeted toxicity (0.2, 0.33) interval while controlling the probability of excessive and unacceptable toxicity below 40%.

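### SAP Section 10 stops reporting the BLRM probabilities that define the MTD, while the SAP still promises an MTD/RP2D estimate; the protocol's QTc category counts are also left out and not itemised

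*SAP*

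**What the plan says.** **MTD.**
- SAP 2.1 keeps as a primary objective: "Estimate the maximum tolerated dose (MTD) and/or a biologically active dose", with the RP2D as the example of the latter. SAP 3.1 (Part 2) still describes a final MTD and RP2D estimate from all DLT-evaluable subjects.
- SAP 5 commits to the estimate: "An estimate of the MTD will be made based on a Bayesian Logistic Regression Model (BLRM) utilizing all DLT-evaluable subjects". It defines the MTD as the dose most likely to have a DLT rate in the target interval (0.20 to 0.33), "while controlling the probability of excessive and unacceptable toxicity below 40" percent.
- SAP 9.6.1 retains the fit: "Subject incidence of DLTs will be used to fit the BLRM model to estimate the probability of having a DLT across dose levels". Protocol 10.5.2 carries the same commitment. SAP 9.6.1 also presents DLT incidence by system organ class and preferred term.
- SAP 10, listing reporting changes made after the study was discontinued, states: "Probability of each TPI and DLT will not be summarized".

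**ECG.**
- Protocol 10.5.2 (Electrocardiogram) plans the number and percentage of subjects by category of maximum QTcF/QTcB change from baseline, and by category of maximum post-baseline value.
- SAP 9.6.6 plans summaries over time and/or changes and percentage changes at scheduled time points, with no categories.
- The only ECG item in SAP 10 is the dropped listing. SAP 5 still defines QTcF and QTcB, and the primary endpoint in SAP 2.1 still covers the incidence of "clinically-significant changes in vital signs, physical examinations, electrocardiograms (ECG) and clinical laboratory tests".

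**The concern.** The SAP promises an estimate, defines it by certain posterior probabilities, fits the model that produces them, and then says they will not be summarized. The same bullet removes the DLT probability by dose, which is the stated purpose of the fit in 9.6.1. SAP 9 specifies no other output for the MTD or RP2D, and nowhere does the SAP say that neither will be declared.

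Two outcomes are therefore open. A dose could be named the MTD with none of its defining probabilities reported, or no dose could be named while the objective still stands. A reader of the report could not tell whether the definition was met.

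The ECG point is smaller. A subject-level count that the protocol promised, bearing on a primary safety endpoint, has no corresponding planned output.

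**Working it through.** **Is there a figure to reproduce?** No. The plan gives no number here, so the check is a cross-reading (above) plus an illustration of whether DLT counts can stand in for the missing probabilities. The actual BLRM cannot be rerun because the doses and reference dose are redacted in the public copy.

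**Model and prior, from Protocol Appendix J and SAP 3.3.** logit(p) = log a + b·ln(dose/reference), where the reference "is 1 of the planned dose selected as the reference dose". I took log a and log b as independent normals.
- Reference dose: central value 0.40 and P(p ≤ 0.05) = 0.05. SD of log a = (logit 0.40 − logit 0.05)/1.645 = (−0.405 + 2.944)/1.645 = 1.544.
- Lowest dose: p = 0.01 with both parameters at their medians. Median b = (logit 0.40 − logit 0.01)/ln(reference/lowest) = 4.190/ln(reference/lowest), which is 1.232, 0.910 and 0.735 for references of 30, 100 and 300 times the lowest dose.
- P(p ≤ 0.40) = 0.90 at the lowest dose then gives SD of log b = 1.610.

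**Assumed, not from the documents:** doses at 1, 3, 10 and 30 times the lowest; cohorts of 1, 1, 3 and 3; the three candidate references; the DLT counts. The posterior was computed on a 601 × 601 grid spanning ±6 prior SDs.

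**Result: P(DLT rate > 0.33) at the top dose, which has 1/3 DLTs in every cell.**

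| Reference (times lowest) | Dose below 0/3 | Dose below 1/3 | Against 0.40 |
|---|---|---|---|
| 30 | 0.43 | 0.59 | both above |
| 100 | 0.16 | 0.45 | opposite sides |
| 300 | 0.12 | 0.37 | both below |

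Across each row, the top-dose count is the same and the probability changes with the data at the dose below. In one of the three rows that decides whether the limit is met.

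Down each column, the whole DLT table is the same and only the reference dose changes, with the prior re-anchored to it. Both columns cross 0.40. Protocol Appendix J lets later model runs move the reference dose, and the Amendment 4 rationale records that it was adjusted after a DLT in an early cohort. The reference behind the final fit therefore has to be named.

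**What the definition can select.** At reference 30 with no DLT below the top dose, 1/3 at the top gives P(excessive) 0.339 and P(unacceptable) 0.087, total 0.426, so the top dose is excluded. Among tested doses the rule then picks the dose below, with P(target) only 0.07. With 1/4 at the top, P(> 0.33) is 0.32 and the rule picks the top dose. Counts alone would not show a reader how weakly a named dose is supported.

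**Sensitivity to the prior.** Reading 0.01 as the true median of p at the lowest dose gives an SD of log b of 1.499, and the 0.426 becomes 0.419. Every cell stays on the same side of 0.40.

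**ECG.** No calculation is needed. Categories by subject maximum appear in Protocol 10.5.2, are absent from SAP 9.6.6, and are not itemised in SAP 10.

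**The case against.** **The cut is disclosed and concerns reporting only.** A reader might infer that the model is not fitted, that results are being concealed, or that escalation decisions were made without it. The documents do not support this. SAP 9.6.1 keeps the fit, SAP 10 states the cut openly, and SAP 7.1 has the BLRM recommendation reviewed with cumulative data at each dose level review. What remains is that the objective, definition and fit were left as they were.

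**The objective reads and/or, and a study stopped early may never reach an MTD.** This is fair, and not reaching an MTD would be no fault. But the SAP gives no other rule supporting an RP2D, and SAP 5 says without qualification that an estimate will be made. If it has been abandoned, the SAP should say so.

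**Protocol 10.5.2 promises a fit, not a table of interval probabilities.** Correct. The case for the table rests on SAP 5's own definition; a credible interval is a recommendation. An explicit statement that no MTD/RP2D will be declared would also resolve the conflict.

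**The figures rest on invented doses, and only one reference in three splits the pair.** True. They show that counts can fail to decide the question; they say nothing about what happened in this trial.

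**ECG.** A reader might infer that the QTc counts were removed with no notice, or that the retained summaries hide how many subjects had a large change. Neither is supported. SAP 1 and the first bullet of SAP 10 give general notice of a reduced scope. SAP 9.6.6 may show absolute values, changes and percentage changes together, which jointly carry much of the subject-level information in small cohorts, and SAP 9.6.2 lists adverse events. The loss is of a promised count and of an itemised entry.

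**Conclusion.** The main point holds as an unreconciled conflict within the SAP: Sections 2.1, 3.1, 5 and 9.6.1 promise an estimate whose defining quantities Section 10 removes from the report. It should be fixed. This finding rests on the text alone.

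The illustration supports a limited claim, under assumed doses, cohorts and reference doses: DLT counts do not by themselves show whether a dose meets the SAP 5 definition. It does not show that any dose in this trial was misjudged.

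The QTc omission is real and secondary: no planned output counts subjects by QTc category, and SAP 10 does not list the change.

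**What to change.** **MTD: choose one.**
1. Delete the TPI/DLT bullet from SAP 10 and add to 9.6.1 one table by dose: DLT-evaluable n, DLTs, posterior DLT rate with a credible interval, and P(target), P(excessive) and P(unacceptable). Name the reference dose used in the final fit.
2. If no MTD/RP2D will be declared, say so in SAP 2.1, 3.1, 5, 9.6.1 and 10.

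**QTc.** Restore the protocol's QTcF/QTcB category counts in SAP 9.6.6 with the category limits stated. At minimum, list their removal in SAP 10.

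**Cost.** About two tables if both outputs are restored, or a few sentences if they are not. The model is already to be fitted, QTcF and QTcB are already defined, and the ECGs are already collected.
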